## **4.3 STUDY OUTCOME MEASURES**

### **4.3.1 Primary Outcome Measure(s)**

The primary outcome measures will be:

1. brain functional connectivity (DMN-Insula and DAN-LIPL) as measured by 7T MRI
2. insular glutamate signal as measured by 7T MRS

Between baseline and visit 2 (week 12) following Olumiant treatment in RA.

### **4.3.2 Secondary Outcome Measure(s)**

The secondary outcome measures will be:

- Changes in clinical phenotype, pain, depression and anxiety as measured by
  - EULAR Disease Activity Score (DAS28)
  - CDAI
  - SDAI
  - 7-Day Symptom Diary (Number Rating Scale)
  - American College of Rheumatology Fibromyalgia Scale
  - McGill Pain Questionnaire
  - Michigan Body Map Regional Pain
  - PROMIS-Depression
  - PROMIS-Anxiety

- PROMIS-Fatigue
- PROMIS-Sleep related impairment
- PROMIS-Physical functioning short form
- PROMIS-Pain inference
- Pain Number Rating Scale
- FACIT Fatigue Scale
- Global Impression of Change (Participant)Cognitive Failures Questionnaire
- Sickness Questionnaire
- Synovitis score (from joint ultrasound)
- Pain sensitivity variables (from QST measures)

- Changes in inflammatory cytokines/chemokines

from baseline (day 0) to Visit 2 (week 12), following Olumiant treatment in RA.

#### **4.4 LABORATORY TESTS**

Sample Type	Visit 1: Baseline	Visit 2 (12 weeks)
SST tube (8.5ml)	✓	✓
PAXgene RNA tube (2.5ml)	✓	✓
EDTA tube (2 x 10ml)	✓	✓
EDTA tubes (4ml)	✓	✓

Blood samples will be processed and analysed as described in the SOAR Lab Protocol.

### **5 Study Medication**

#### **5.1 OLUMIANT TREATMENT SCHEDULE & ADMINISTRATION**

Olumiant (4mg) will be administered in line with standard of care guidance. This is the standard dose in line with license for use in active moderate to severe RA. A dose adjustment from 4mg to 2mg is permitted during the study depending on side-effects.

##### **5.1.1 Olumiant Treatment After the Study**

At the end of their study involvement, all participants will be returned to NHS standard care. Arrangements will be made such that all participants continue NHS standard care with Olumiant without interruption.

#### **5.2 ONCOMITANT MEDICINES**

##### **5.2.1 Permitted Concomitant Medicines**

Concomitant medicines are permitted at the PIs discretion. Maintenance of stable doses of conventional synthetic DMARDs, nonsteroidal anti-inflammatory drugs, analgesics, or glucocorticoids ( $\leq 10$  mg of prednisone or the equivalent per day) will be permitted. Intra-articular and intramuscular triamcinolone can be used, but not within 8 weeks of the baseline and 12-week assessments.

### **5.2.2 Prohibited Concomitant Medicines**

Biologic disease modifying antirheumatic drug therapy with adalimumab, etanercept, golimumab, infliximab, certolizumab, abatacept, tocilizumab, sarilumab, rituximab, tofacitinib, apremilast or upadacitinib.

## **5.3 DISCONTINUATION OF STUDY MEDICINES**

The study medication should be permanently and immediately discontinued in case of the following situations:

1. Serious infection requiring hospitalisation, including sepsis, tuberculosis and opportunistic infections such as invasive fungal infections, which rule out the continuation of the study drug if determined so by the Investigator
2. Clinically significant abnormal laboratory result(s) or AE(s), which rule out continuation of the study drug, as determined by the Investigator
3. The Investigator believes it is in the best interest of the subject.
4. The participant requests withdrawal from the study.
5. Commencement of prohibited medicines.
6. Any other potentially serious condition as judged by the investigator which may place the participant at additional risk should they continue within the study.

Participants may also be withdrawn from the study in the event they are significantly non-compliant with study procedures to the extent that the participant would be at risk for continued participation in the trial as determined by the investigator.

At the end of their study involvement, all participants will be returned to NHS standard care. Arrangements will be made such that all participants continue with NHS standard care treatment with Olumiant without interruption.

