### **3.2 INCLUSION CRITERIA**

- Adults  $\geq$  18 years  $<$  75 years.
- Clinical diagnosis of RA
- Selected to start Olumiant by their usual rheumatology clinical team in line with local guidance (previous failure of at least 2 DMARDs and moderate to severe disease active disease)
- Right-handed (to reduce neuroimaging heterogeneity)

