### **3.4 IDENTIFICATION OF PARTICIPANTS AND CONSENT**

Patients with active RA attending clinics in NHS Greater Glasgow and Clyde who are scheduled to begin Olumiant as part of their standard NHS clinical care will be asked to contribute to this study by their point of care team. The direct care team will notify patients of the study, provide a participant information sheet and seek their consent for the research team to contact them by telephone. at least 24 hours later to gauge their interest in the study and allow them to ask any questions. Eligibility will be confirmed by a medically qualified investigator. A record will be kept on the CRF detailing if the telephone call was made, if contact was indeed established and the outcome of the telephone call.

If the patient is interested and eligible, they will be invited to attend Visit 1 where they will first undertake informed consent. At this meeting, subjects will be asked again if they have any questions and those who wish to participate will be asked to sign the consent form. Two copies will be signed (one each for the participant and the site file) and a copy of the signed consent form will be inserted into the patient's record or scanned into the electronic patient record (EPR). A letter will be sent to the patient's GP to inform them of their participation in the study.

Consent will be taken by a member of the research team.

Reasonable travel expenses will be reimbursed.

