### **3.5 WITHDRAWAL OF SUBJECTS**

Participants can decide to withdraw from the study at any time without providing a reason. The participant needs to request this formally and a withdrawal document will be completed and signed by the research staff. They have the option to either withdraw from the study completely or from parts of it.

Participants will have the option to remain in the study irrespective of stopping treatment. The Chief Investigator (CI) or co-investigators also have the right to withdraw patients from the study if deemed in the best interests of the patient or in the event of Adverse Events (AEs), protocol violations, loss of capacity for continuous consent, administrative or other reasons. Full details of withdrawal will be recorded on the electronic Case Report Form (eCRF).

Participants may decide to withdraw their initial consent for this study, at this point no further information regarding the participant will be collected. Data relating to the patient that has been collected up to the point of withdrawal will still be used unless the participant specifies they do not wish this to happen. Any stored blood samples that can still be identified as the participants will be destroyed if the participants wish this.

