### **5.3.1 Supply of Study Treatment**

The study site will be responsible for procurement of all Olumiant via usual NHS supply mechanisms for medicines.

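### Section 5.3 item 4 makes a request to leave the study a reason to stop Olumiant permanently, although the drug is the patient's own NHS treatment and sections 5.1.1 and 5.3 say it continues

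*Combined protocol and SAP*

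**What the plan says.** Section 5.3 sets out six situations under the lead-in "The study medication should be permanently and immediately discontinued in case of the following situations". The fourth reads, in full, "The participant requests withdrawal from the study".

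The closing paragraph of the same section deals with what happens when a participant's involvement ends: "Arrangements will be made such that all participants continue with NHS standard care treatment with Olumiant without interruption". Section 5.1.1 carries almost the same sentence: "Arrangements will be made such that all participants continue NHS standard care with Olumiant without interruption".

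Three other places fix the status of the drug:

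- Section 3.2 admits patients "Selected to start Olumiant by their usual rheumatology clinical team in line with local guidance".
- Section 3.4 describes them as patients "who are scheduled to begin Olumiant as part of their standard NHS clinical care".
- Section 5.3.1 states: "The study site will be responsible for procurement of all Olumiant via usual NHS supply mechanisms for medicines".

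On leaving the study, section 3.5 says: "Participants can decide to withdraw from the study at any time without providing a reason". It also lets a participant stay in the study after coming off treatment. Section 13.2 names the study and the study treatment as two separate things from which consent may be withdrawn.

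**The concern.** Item 4 joins two decisions that the rest of the protocol keeps apart: leaving the research and stopping the drug. Under the lead-in to the list, the first leads to a permanent and immediate end to the second. The continuation sentences in 5.1.1 and 5.3 direct the opposite for the same person at the same moment.

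What is at stake is the care of the patient who leaves. These patients have moderate to severe active disease and at least two failed DMARDs (section 3.2). A literal reading would take away a drug that their own clinical team prescribed, with no clinical reason. It would also attach a treatment consequence to a choice that section 3.5 presents as free and needing no explanation.

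**Working it through.** The protocol gives no figure on this point, so the check is a comparison of the text.

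**Step 1: what each of the six triggers in 5.3 rests on.**

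| Item | Trigger | Ground |
|---|---|---|
| 1 | Serious infection | Clinical, by investigator judgement |
| 2 | Significant laboratory abnormality or adverse event | Clinical, by investigator judgement |
| 3 | Best interest of the participant | Investigator judgement |
| 4 | Request to leave the study | The request alone |
| 5 | Start of a prohibited medicine | Medication |
| 6 | Other potentially serious condition | Clinical, by investigator judgement |

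Four items rest on the investigator's judgement about the patient, one on a medicine and one on the request alone: 4 + 1 + 1 = 6.

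**Step 2: whether the continuation sentence covers someone who withdraws.** In both places it applies when study involvement ends and refers to all participants. It is not limited to those who complete Visit 2. A participant who withdraws completely has ended their involvement, so the sentence applies to them.

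**Step 3: whether the drug in the lead-in can differ from the drug that continues.** It cannot. Olumiant is the only study medication. It is selected by the usual team (3.2), scheduled as standard NHS care (3.4), given under standard-of-care guidance (5.1) and supplied wholly through NHS routes (5.3.1). Stopping the study medication means stopping the patient's own Olumiant.

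**Step 4: the two instructions for one event.**

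| Event | Lead-in and item 4 of 5.3 | 5.1.1 and close of 5.3 |
|---|---|---|
| Participant asks to leave the study completely | Stop Olumiant at once and for good | Continue Olumiant with no break |

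Both cannot be carried out.

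**Step 5: whether a rule of precedence settles it.** For items 1, 2, 3 and 6 a clinical reason to stop plainly outranks a general sentence about continuing, and item 5 has a medication ground. Item 4 offers nothing of the kind, so the text does not say which instruction prevails.

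**Step 6: consistency with the withdrawal and consent sections.** Section 3.5 describes a withdrawal form, the handling of data and the fate of stored samples. It mentions no change to treatment. Sections 3.5 and 13.2 both treat study and treatment as separable. Item 4 fits neither.

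**The case against.** The strongest reply is that 5.3 answers the question itself. Its closing paragraph and 5.1.1 are specific, repeated handover instructions, and someone who withdraws is exactly the person they describe. Staff would probably follow them. Prescribing and supply sit with the NHS, and nothing in the protocol describes a mechanism for stopping the drug on withdrawal.

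There is also textual support for a milder reading. Item 6 turns on the risk of remaining in the study, and the paragraph after the list says participants may *also* be withdrawn from the study. Both suggest that the list mixes reasons for stopping the drug with reasons for leaving the study. On that reading, item 4 only ends Olumiant's status as study medication.

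Much of this stands as a comment on likelihood. The list probably does mix two ideas, and many clinicians would continue the drug. It does not remove the defect. The lead-in governs the drug, the word for permanence has no sense if only a label is being removed, and items 1 and 2 are plainly about the drug. The closing sentence is one side of the conflict and does not resolve it.

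Two further replies deserve an answer.

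- **Participant information sheet.** It is not among the documents, so what patients are told about Olumiant after leaving cannot be checked. That is so, and the point here is limited to what the protocol directs.
- **Partial withdrawal.** Section 3.5 allows withdrawal from parts of the study, and item 4 does not say whether it applies then. That is a fair observation. It adds to the ambiguity, and deleting item 4 resolves it.

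It is also argued that limiting the continuation sentence goes beyond the defect. Section 3.5 expects that some participants may have stopped treatment, and for them a promise of uninterrupted Olumiant is wrong as it stands. The limit is justified.

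**Conclusion.** The concern holds. Item 4 is wrong as written: for a participant who leaves, it directs the opposite of 5.1.1 and of the close of 5.3, and it has no clinical basis.

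The extent is one of six triggers, together with one continuation sentence that appears twice. The number of participants affected cannot be stated. The planned sample is 20 and section 7.6 allows for 3 dropouts, but that allowance is not split by reason, so no figure is drawn from it.

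No effect on the primary endpoints, sample size or analysis is claimed. For complete withdrawal of consent, section 3.5 ends further data collection. For partial withdrawal the text is silent on whether item 4 applies, and nothing is inferred.

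The conclusion rests on reading the lead-in literally and on there being no study-specific supply of Olumiant, which 5.3.1 supports. It should be fixed as a matter of participant care and free withdrawal.

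**What to change.** Delete item 4 from the list in 5.3. If a line on withdrawal is wanted there, say that leaving the research does not by itself change Olumiant treatment, which remains a decision for the patient and the usual rheumatology team.

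In 5.1.1 and the closing paragraph of 5.3, limit the continuation sentence to participants who are still taking Olumiant and for whom it remains clinically appropriate. Sections 3.5 and 13.2 need no change.

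The cost is a wording amendment to one list item and one sentence in two places, through the approval route in section 12. Sample size, visits and analysis are unaffected.

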### **5.3.1 Supply of Study Treatment**

The study site will be responsible for procurement of all Olumiant via usual NHS supply mechanisms for medicines.

## **6 PHARMACOVIGILANCE**

### **6.1 DEFINITIONS OF ADVERSE EVENTS (AEs)**

Any untoward medical occurrence in a subject to whom a medicinal product has been administered, including occurrences which are not necessarily caused by or related to that product.

### **6.2 SERIOUS ADVERSE EVENT (SAE)**

Any adverse event or adverse reaction that:

- a) Results in death
- b) Is life threatening
- c) Requires hospitalisation or prolongation of existing hospitalisation
- d) Results in persistent or significant disability or incapacity
- e) Consists of a congenital anomaly or birth defect
- f) Is otherwise considered medically significant by the investigator
- g) Important adverse events/reactions that are not immediately life-threatening or do not result in death or hospitalisation but may jeopardise the subject or may require intervention to prevent one of the other outcomes listed in the definition above

### **6.3 RECORDING AND REPORTING OF ADVERSE EVENTS**

Reports of Serious Adverse Events (SAE), drug exposure during pregnancy, non-serious Adverse Events (AE) and misuse and abuse of the study drug, other medication errors and uses outside of what is foreseen in the protocol (irrespective if a clinical event has occurred) should be submitted to the Research Ethics Committee (REC) using the Non-CTIMP safety report to REC form.

Only reports of SAEs and non-serious AEs that are 1. related to the study (i.e. they resulted from administration of any of the research procedures) and 2. unexpected (i.e. not listed in the protocol as an expected occurrence) should be submitted.

These should be sent within 15 days of the CI becoming aware of the event. There is no requirement for annual safety reports in addition to the information provided through the annual progress report.

#### **Related Unexpected Serious Adverse Event (RUSAE)**

Any SAE thought to be related to a trial specific procedure performed on that subject that is thought to be unexpected; that is the event is not listed within the protocol or would not be expected to occur when carrying out the trial specific procedure in normal clinical practise.

#### **Recording and reporting of adverse events**

The study is considered to be of low risk and is primarily an observational study. The MRI scanning procedure is the principal trial specific procedure and safety reporting will be focussed around this procedure

Adverse events and serious adverse events will be collected only during the period of time the participant attends clinic for their MRI scan i.e. from the time the participant begins preparation for the scan until 24 hours post scan.

In addition to Sponsor requirements the investigators have a contractual agreement with the MAH to report any SARs suspected to be related to olumiant within 15 days of investigator awareness. These events should be recorded and reported in line with the manufacturers requirements.

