**Visit 2 (Week 12 ± 14 days)**

- Clinical assessment
- Sickness behaviour questionnaires
- Bloods for immunophenotyping
- 7T MR sequences
- Optional joint ultrasound
- Optional quantitative sensory testing

Olumiant treatment

**SOAR - Exploiting Leading Edge 7T MRI Brain Imaging to Decipher Olumiant's Mode of Analgesic Action in Rheumatoid Arthritis**

GLASGOW CLINICAL TRIALS UNIT

FORM 51.001A

V7.0

Study Procedure	Visit 1 - Screening & Baseline	Visit 2 - 12 week
Inclusion/exclusion criteria	✓	
Informed consent	✓	
EULAR Disease Activity Score (DAS28)	✓	✓
ACR/EULAR Classification Criteria for RA	✓	
CDAI	✓	✓
SDAI	✓	✓
7-Day Symptom Diary (Numeric Rating Scale)	✓	✓
American College of Rheumatology Fibromyalgia Scale	✓	✓
McGill Pain Questionnaire	✓	✓
Michigan Body Map Regional Pain	✓	✓
PROMIS-Depression	✓	✓
PROMIS-Anxiety	✓	✓
PROMIS-Fatigue	✓	✓
PROMIS-Sleep related impairment	✓	✓
PROMIS-Physical functioning short form	✓	✓
PROMIS-Pain inference	✓	✓
Pain NRS Pain Number Rating Scale	✓	✓
FACIT-Fatigue Scale	✓	✓
Global Impression Of Change (participant)		✓
Cognitive Failures Questionnaire	✓	✓
Sickness Questionnaire	✓	✓

**SOAR - Exploiting Leading Edge 7T MRI Brain Imaging to Decipher Olumiant's Mode of Analgesic Action in Rheumatoid Arthritis**

GLASGOW CLINICAL TRIALS UNIT

FORM 51.001A

V7.0

Demographics	✓	
BMI	✓	
Drug Assessment	✓	✓
Past Medical History	✓	
Blood sample for immunophenotyping*	✓	✓
7T magnetic resonance protocol	✓	✓
Ultrasound of joints**	✓	✓
Quantitative sensory testing (QST)**	✓	✓
Recording of Adverse Events		✓

\* Blood sample schedule outlined in 4.4 LABORATORY TESTS

\*\* Consent to these procedures is optional

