#### 4.1.1 Screening & Baseline (Day 0)

- Informed consent
- Review of inclusion / exclusion criteria
- ACR/EULAR Classification Criteria for RA
- EULAR Disease Activity Score (DAS28)
- CDAI
- SDAI
- 7-Day Symptom Diary (Number Rating Scale)
- American College of Rheumatology Fibromyalgia Scale
- McGill Pain Questionnaire
- Michigan Body Map Regional Pain
- PROMIS-Depression
- PROMIS-Anxiety
- PROMIS-Fatigue
- PROMIS-Sleep related impairment
- PROMIS-Physical functioning short form
- PROMIS-Pain inference
- Pain Number Rating Scale
- FACIT Fatigue Scale
- Cognitive Failures Questionnaire
- Sickness Questionnaire
- 7T MRI protocol
- Ultrasound of joints of interest
- Quantitative sensory testing (QST)
- Blood draw for immunophenotyping
- Demographics
- BMI
- Drug Assessment
- Past Medical History

Estimated visit time 4 hours

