#### 4.1.2 VISIT 2 : Week 12 ± 14 days

- ACR/EULAR Classification Criteria for RA
- EULAR Disease Activity Score (DAS28)
- CDAI
- SDAI
- 7-Day Symptom Diary (Number Rating Scale)
- American College of Rheumatology Fibromyalgia scale

- McGill Pain Questionnaire
- Michigan Body Map Regional Pain
- PROMIS-Depression
- PROMIS-Anxiety
- PROMIS-Fatigue
- PROMIS-Sleep related impairment
- PROMIS-Physical functioning short form
- PROMIS-Pain inference
- Pain Number Rating Scale
- FACIT Fatigue Scale Global Impression of Change (participant)
- Cognitive failures questionnaire
- Sickness Questionnaire
- 7T MRI protocol
- Ultrasound of joints of interest
- Quantitative sensory testing (QST)
- Blood draw for immunophenotyping
- Drug assessment

Estimated visit time 3.5 hours

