#### Recording and reporting of serious adverse events

Where an SAE requires recording; full details including the nature of the event, start and stop dates, severity, relationship to research product and/or trial procedures, and the outcome of the event will be recorded in the patient's medical notes and CRFs.). These events will be monitored and followed up until satisfactory resolution and stabilization.

SAEs should be assessed to determine if the event is related to the MRI scanning procedures and assessed for expectedness against the list of expected events detailed below.

Where an event meets the criteria of an SAE and is both:

Related: that is, it resulted from administration of study medicines or any of the research procedures,

And

Unexpected: that is against the procedure events listed below as an expected occurrence.

The SAE is considered a Related and Unexpected Serious Adverse Event (RUSAE) and must be reported to the Sponsor.

The assessment of causality and expectedness must be carried out by an authorised clinician.

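### Two safety rules in the protocol disagree: the schedule ticks adverse event recording at only one of the two scan visits, and section 6.3 has two scopes for a related SAE (minor)

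*Combined protocol and SAP*

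**What the plan says.** **Collection window.** Section 6.3 (Recording and reporting of adverse events) states: "Adverse events and serious adverse events will be collected only during the period of time the participant attends clinic for their MRI scan". The window opens when preparation for the scan begins and closes 24 hours after it. The next subsection makes recording of adverse events in that window mandatory.

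**Schedule.** In the Schedule of Assessments the row "7T magnetic resonance protocol" is ticked at Visit 1 and Visit 2. The row "Recording of Adverse Events" is ticked at Visit 2 only. The activity lists in 4.1.1 and 4.1.2 both include the 7T protocol, and neither includes adverse event recording.

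**Relatedness and expectedness.** Within 6.3, the subsection on serious adverse events first says: "SAEs should be assessed to determine if the event is related to the MRI scanning procedures". It then sets the criterion for a Related and Unexpected SAE (RUSAE): "Related: that is, it resulted from administration of study medicines or any of the research procedures", together with "Unexpected: that is against the procedure events listed below as an expected occurrence". The only list that follows covers MRI hazards. The separate RUSAE definition in 6.3 refers to a trial-specific procedure. The opening of 6.3 limits reports of SAEs and non-serious AEs to the Research Ethics Committee (REC) to those arising from research procedures. Every RUSAE goes to the Sponsor's pharmacovigilance office within 24 hours. SAEs suspected to be due to Olumiant go separately to the MAH within 15 days.

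**The concern.** The protocol names the MRI scan as its principal trial-specific procedure and centres safety reporting on it. A schedule that shows no recording step at the first of two scans is at odds with that. Site staff commonly work from the schedule, and the SAE summary in section 7.4 can only count what was captured.

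The second conflict concerns who is told about an event. A clinician assessing an SAE that occurs in a scan window and is attributed to Olumiant would reach different answers from two parts of the same section: a 24-hour report to the Sponsor, or no RUSAE at all. The assessment of causality and expectedness rests with that clinician, who needs one rule.

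**Working it through.** There is no planned figure to reproduce. The check is a comparison of the texts, with simple counts.

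**1. Scan windows against ticks**

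| Source | Visit 1 | Visit 2 |
|---|---|---|
| 7T scan, Schedule of Assessments | ticked | ticked |
| 7T scan, lists in 4.1.1 and 4.1.2 | listed | listed |
| Collection window under 6.3 | yes | yes |
| Adverse event recording, Schedule of Assessments | not ticked | ticked |
| Adverse event recording, lists in 4.1.1 and 4.1.2 | not listed | not listed |

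Section 6.3 does not say that the rule applies to every scan. That follows because a scan is scheduled at each visit. Each participant therefore has two windows and one tick. A fault in reading the table is unlikely: the row for the participant's Global Impression of Change has the same layout, and 4.1.1 and 4.1.2 confirm that it belongs to Visit 2 only.

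With 20 participants (section 7.6), 20 Visit 1 windows have no tick. This counts missing ticks, not missed events.

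**2. One event under each rule**

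Take a serious infection that occurs in a scan window and is attributed to Olumiant. Section 5.3 foresees serious infection as a reason to stop the drug.

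| Rule in 6.3 | Related? | Consequence |
|---|---|---|
| Opening paragraphs (reports to the REC) | No: research procedures only | Not reportable to the REC |
| RUSAE definition | No: trial-specific procedure only | Not a RUSAE |
| SAE subsection, first instruction | No: MRI procedures only | No relation to record |
| SAE subsection, RUSAE criterion | Yes: study medicines included | Unexpected, because the list has MRI hazards only; RUSAE, Sponsor within 24 hours |
| MAH subsection | Suspected drug cause | MAH within 15 days, whichever reading is used |

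Because the expected list contains no drug reactions, any Olumiant-caused SAE in the window counts as unexpected under the RUSAE criterion, however well recognised it is. The Sponsor and Chief Investigator review expectedness before anything goes to the REC, so the REC submission might be stopped. That review comes after the 24-hour report.

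**3. How often this could arise**

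The protocol gives "Estimated visit time 4 hours" for Visit 1 and "Estimated visit time 3.5 hours" for Visit 2. Assume that preparation begins no earlier than the visit and that the scan ends no later than the visit. The windows are then at most 4 + 24 = 28 hours and 3.5 + 24 = 27.5 hours. The sum is 55.5 hours, or 55.5/24 = 2.3 days per participant, and not all of it is on treatment. Over 20 participants that is at most 20 × 2.3 = 46 participant-days. The documents give no SAE rate, so no expected number of events is calculated.

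**The case against.** **Schedule.** Section 3 describes the schedule as a summary of the design. The binding text is 6.3, which requires recording in any scan window, ticked or not, and the protocol has participants monitored throughout the MRI. The window also closes 24 hours after the scan, so it cannot be completed at Visit 1, and the Visit 2 tick could be meant as retrospective recording. The first argument stands: a reader might infer that Visit 1 scan events will go unrecorded, and the documents do not support that. The retrospective reading is possible, but no text states it, and recall after about 12 weeks fits poorly with 24-hour reporting.

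**Relatedness.** The SAE subsection is the operative rule and the most inclusive one, so a clinician who follows it simply reports. The error is toward over-reporting, and the MAH route catches drug-related SAEs in any case. This stands, and it rules out the inference that drug-related SAEs would go unreported. It does not remove the contradiction. The protocol describes the MAH duty as additional to Sponsor requirements, so that duty cannot settle what the Sponsor requires.

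**Two further readings to avoid.** A reader might conclude that the lack of a routine question about SAEs between the two scans is itself an error. The restriction to scan windows is explicit and defensible for standard-care treatment, and the agreement with the MAH, which may cover this, is not among the documents. A reader might also assume that only the Visit 2 window can hold an on-drug event. The protocol does not say that the first dose waits until 24 hours after the Visit 1 scan.

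**Conclusion.** The protocol is wrong as written on both points, and both are minor. One of the two scan windows per participant has no recording step in the schedule, although 6.3 requires recording there. Section 6.3 also gives incompatible answers on whether an Olumiant-caused SAE in a scan window is a RUSAE. The practical effect is limited to a possible omission at Visit 1 by staff guided by the schedule, and to a rare, mostly excess, report to the Sponsor. Rarity is a judgement from the short windows and the 20 participants, not from a documented event rate. The primary imaging analysis and all efficacy endpoints are unaffected. Only the descriptive SAE summary in 7.4 depends on what is captured.

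**What to change.** 1. In the Schedule of Assessments, tick adverse event recording at both visits. Add the item, with its window from scan preparation to 24 hours after the scan, to 4.1.1 and 4.1.2.

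2. Use one definition of related throughout 6.3. The simplest course is to delete the reference to study medicines from the RUSAE criterion, so that it agrees with the RUSAE definition and the opening of 6.3, and to direct Olumiant-related SAEs to the MAH subsection. The downside is that such events lose the 24-hour Sponsor report and keep only the 15-day MAH route. If the Sponsor wants that report, keep the words, extend the other two passages to match, and add a drug expectedness reference beside the MRI list. Under either option, word the MRI-only causality instruction to fit the scope chosen.

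The cost is wording changes in one protocol amendment, with REC and R&D approval under section 12, which could be combined with another amendment. No new visit or test is needed.
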